Patient treated for indicated actionable mutation guided by Foundation One, CDx Guardant 360, or other NGS tumor analysis outcome report- according to study algorithm-

Study follow-up:
Treatment Received
Adverse Events
Response Rate
Progression-Free Survival
Quality of Life outcomes

1.0 Introduction and Background

Precision medicine is a rapidly growing field with the potential to bypass ineffective treatments and target specific genetic mutations present in cancer cells. Although clinicians have access to increasing amounts of data regarding tumor genomics, it can be problematic to identify a primary driver mutation and the optimal treatment.(Paolillo, Londin, & Fortina, 2016). Due to this complexity many clinicians are uncomfortable interpreting genomic sequencing results from next generation sequencing assays (“NGS”) [J. Clin Oncol 2014, 32, 1317-1323]. A recent survey of providers at a major academic center revealed that more than half the providers were uncomfortable interpreting the information from a genomic test [Oncotarget 2017; 8; 27145-27154]. Various strategies have been used to facilitate the proper interpretation of genomic data including in-person and virtual molecular tumor boards but the limited experience and large numbers of permutations with multiple genetic mutations in a single tumor make the identification of one or more driver mutations in a particular patient largely a matter of an educated guess at best. This has the effect of discouraging the use of targeted therapies, that may provide benefit, in patients who have exhausted standard of care treatments. Frequently, physicians prescribe medications off-label in an effort to delay progression of disease. Off label prescribing involves prescribing a medication for an indication other than the condition for which there is FDA approval.Those physicians prescribing targeted therapies off label, based on NGS results face other challenges. These include lack of access to available drugs, costs of available drugs, and differing reimbursement policies among insurance companies, among others (Messner et al., 2016)

At Wake Forest Baptist Comprehensive Cancer Center (“WFBCCC”), solid tumors are most often analyzed using Foundation One CDx, an FDA approved NGS Cancer Profiling Test, while liquid samples are primarily analyzed using an assay from Guardant 360. Other NGS tests employed for tumor analysis include Caris Molecular Intelligence® Comprehensive Tumor Profiling. Results from the testing include any identified ,or actionable, genetic mutations and any known drugs with suspected or proven efficacy for treating these mutations. Off-label drug treatment options are included in the lab report. Additionally, any known drugs that lack efficacy for the tumor are outlined in the report. For many of the identified mutations, however, no off-label drug option is available.

According to WFBCCC data, 9.4% of patients have five or fewer mutations identified in their cancer sample, 48.3% have 10 or fewer, 79.1% have 15 or fewer and 87.9% of patients who have NGS testing exhibit 20 or more genetic mutations in their cancer sample. For many of these mutations, however, no off-label drug is available.

The goal of the current pragmatic trial is to evaluate the impact of a simple method of selecting a treatment approach for identified mutations on subjects' progression free

survival (PFS) by assigning treatment in a balanced manner when no identified optimal off-label treatment is defined. The study also intends to collect information on barriers that providers encounter when prescribing treatment options using the NGS reports and to measure patients' quality of life before, after, and during treatment.

2.0 Objectives

2.1 Primary Objective

- 2.1.1 To estimate the progression-free ratio, as defined by the progression-free survival time on study treatment divided by the progression-free survival time on the last treatment received by patient, for an identified actionable mutation, who will be treated with an off-label treatment off label therapy based on a simplified selection methodology using the NGS results.

2.2 Secondary Objectives

- 2.2.1 To estimate patient response rate on off-label treatments for actionable mutations based on NGS results.
- 2.2.2 To estimate overall survival (OS) for patients treated with off-label treatments for actionable mutations based on NGS results.
- 2.2.3 To describe the safety of using off-label or other experimental treatments for patients with actionable mutations based on NGS results.

2.3 Exploratory Objectives

- 2.3.1 To describe health related quality of life in patients undergoing off-label treatment targeting genetic mutations, as measured by the PROMIS-29 Overall Health-Related Quality of Life, Including 4-Item Anxiety Subscale..
- 2.3.2 Using the Satisfaction with Medical Decision Scale, to describe patient satisfaction with decision to pursue off-label treatment.
- 2.3.3 To identify types of actionable mutations with available targeted treatment occurring in cancer patients.
- 2.3.4 To characterize the historical treatment regimens for these patients relative to the targetable mutation.

ClinicalTrials.gov: NCT04111107

- 2.3.5 To describe patient clinical and demographic characteristics of those with actionable mutations based on NGS results.
- 2.3.6 To identify barriers to treatment based on NGS results.

3.0 Patient Selection

3.1 Inclusion Criteria

- 3.1.1 Cancer patients at Wake Forest Baptist Comprehensive Cancer Center and its satellites who have next generation DNA sequencing results on their tumor biopsy or surgically resected tissue and/or blood samples and/or consent to the WFCCC Precision Oncology Registry to use their information for research.
- 3.1.2 Actionable mutation (defined as a mutation or gene amplification for which an off-label therapy is identified on the patient's NGS report for which NCCN guidelines do not recommend a specific treatment in the particular disease or for which there is no documentation in the patient's medical record of clinical data demonstrating lack of activity with the targeting of the specific mutation or amplification in the patient's specific disease) uncovered by the genomic sequencing of a tumor or those that have undergone liquid biopsy assay of their tumor genomic, performed by Wake Forest or another and who are medically able to receive targeted therapy based on those results.
- 3.1.3 Sequencing on a sample collected within 3 months prior to registration is strongly encouraged but must have been performed within the 12 months prior to registration.
- 3.1.4 Patients must have progressed through at least two lines of treatment, or are not candidates for or unwilling to receive any standard therapies. Patients who have received treatment on the present protocol who have progression of disease may be recruited to the trial for treatment using another targeted therapy provided that they fullfil the other criteria for participation in the trial. If a patient discontinues treatment on this protocol they can be considered for further participation in this trial provided they meet all of the eligibility criteria and are eligible for re-registration and re-consent.
- 3.1.5 ECOG of ≤ 3
- 3.1.6 Life expectancy of greater than 6 weeks

ClinicalTrials.gov: NCT04111107

3.1.7 The effects of the drugs used for cancer treatment on the developing human fetus are unknown. For this reason and because of the possibility that the agents are teratogenic, women of child-bearing potential and men must agree to use adequate contraception (hormonal or barrier method of birth control; abstinence) prior to study entry and for the duration of study participation. Should a woman become pregnant or suspect she is pregnant while participating in this study, she should inform her treating physician immediately.

3.2 Exclusion Criteria

- 3.2.1 Patients who have had or will receive chemotherapy or radiotherapy to major bone marrow bearing sites within 2 weeks prior to receiving treatment on the study.
- 3.2.2 Patients who have not recovered from toxicity of prior treatment if such toxicity will preclude treatment with the proposed targeted agent.
- 3.2.3 Patients may not be receiving any other investigational agents.
- 3.2.4 Uncontrolled intercurrent illness including, but not limited to ongoing or active infection, symptomatic congestive heart failure, unstable angina pectoris, cardiac arrhythmia, or psychiatric illness/social situations that would limit compliance with study requirements.
- 3.2.5 Pregnant women are excluded from this study because of the potential for teratogenic or abortifacient effects. Because there is an unknown but potential risk for adverse events in nursing infants secondary to treatment of the mother with the targeted agent, breastfeeding should be discontinued if the mother is treated with the targeted agent.

3.3 Inclusion of Women and Minorities

- 3.3.1 Women and men of all races and ethnicity who meet the above-described eligibility criteria are eligible for this trial.
- 3.3.2 Based on WFBCCC population estimates, we expect approximately 50% of participants to be female, 13% Black or African American, and 6.5% of participants to be of Hispanic ethnicity. 3.0% of the remaining minority population will be comprised of individuals of other ethnicities. Should we not meet or exceed these estimates, the PI will engage the Cancer Center Health Equity Advisory Group to discuss strategies to enhance recruitment in these target populations. However, the population will

ClinicalTrials.gov: NCT04111107

change over time and these estimates may not reflect future ancestral distributions in the future.

4.0 Registration Procedures

All patients entered on any WFBCCC trial, whether treatment, companion, or cancer control trial, **must** be linked to the study in EPIC within 24 hours of Informed Consent. Patients **must** be registered prior to the initiation of treatment.

You must perform the following steps in order to ensure prompt registration of your patient:

1. Complete the Eligibility Checklist (Appendix A)
2. Complete the Protocol Registration Form (Appendix B)
3. Alert the Cancer Center registrar by phone, *and then* send the signed Informed Consent Form,
4. Eligibility Checklist and Protocol Registration Form to the registrar, either by fax or e-mail.

Contact Information:

Protocol Registrar [contact]

Protocol Registrar [contact]

Protocol Registrar E-MAIL ([contact])

*Protocol Registration is open from 8:30 AM - 4:00 PM, Monday-Friday.

5. Fax/e-mail ALL eligibility source documents with registration. Patients **will not** be registered without all required supporting documents.

Note: If labs were performed at an outside institution, provide a printout of the results. Ensure that the most recent lab values are sent.

To complete the registration process, the Registrar will:

- assign a patient study number
- assign the patient a drug and dose
- register the patient on the study

5.0 Study Outcomes and Study Measures

5.1 Primary Outcome

ClinicalTrials.gov: NCT04111107

5.1.1 Progression free ratio, defined as the duration of time from start of treatment to the time of progression divided by the duration of time from the last treatment received pre-trial to the time of progression on that treatment. Those that die before progression or are lost to follow-up will be non-evaluable for the primary objective.

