	Pre-Study ^a	Cycle 2, Day 1	Day 1; every even cycle (after cycle 2)	End of Treatment ±7 days	Follow up for Safety (30+ days after last treatment) required only if pt has treatment related AEs at end of treatment visit
Informed Consent	X				
Demographics	X				
Medical History	X				
Concurrent Meds	X				
Physical Exam	X	X	X	X	X
Vital Signs	X	X	X	X	X
Performance Status	X	X	X	X	X
Bone Marrow Biopsy ^h	X	X	X	X	
Imaging ^d	X	X	X ^f	X	
CBC w/diff, platelets ^e	X	X	X	X	X
Serum Chemistry ^b	X	X	X	X	X
B-HCG ^c	X				
Dose Adjustment Form		X	X		
Adverse Event Evaluation		X	X	X	X
Survival Status/Telephone Follow up ^g					X
PROMIS 29	X	X		X	
Satisfaction with Medical Decision Scale	X	X		X	
Patient Reported Outcome- Demographics/Health Literacy	X				

^a Pre-study requirements listed in table must be completed **within** 30 days prior to registration. Imaging demonstrating disease progression should be completed within 60 days of registration. Imaging should be repeated if the scan occurred more than 30 days prior to treatment initiation..

^b Albumin, alkaline phosphatase, total bilirubin, bicarbonate, BUN, calcium, chloride, creatinine, glucose, potassium, total protein, SGOT[AST], SGPT[ALT], sodium.

^c Serum pregnancy test within 10 days of Pre-study visit (women of childbearing potential only).

^d Imaging will be performed as part of SOC for solid tumors every other cycle, however due to patients on different drug treatment regimen, this may occur at 6 weeks ±2 weeks, 8 weeks ± 2 weeks or 12 weeks ± 2 weeks. Not required for leukemias. As clinically indicated in Multiple myeloma.

^e Labs will be performed in accordance with the recommendations of the prescribing instructions for the drug that is utilized

^f If treatment is discontinued for reasons other than progression, imaging will be performed on the same schedule as was utilized while patient was receiving treatment until progression.

^g Survival and information related to cancer treatment received after the study and disease status is monitored bimonthly via telephone contact or EMR review after treatment termination. Medical record review will be performed to coincide with the bimonthly telephone call to obtain information regarding evidence and of relapse (as documented on CT, PET, biopsy, etc).

^h If clinically indicated bone marrow biopsy will be repeated to evaluate response to therapy.

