8.1.2 Methods for Evaluation of Measurable Disease

- **Method(s) for obtaining measurements:**

All measurements should be taken and recorded in metric notation using a ruler or calipers. All baseline evaluations should be performed as closely as possible to the beginning of treatment and never more than 4 weeks before the beginning of the treatment.

The same method of assessment and the same technique should be used to characterize each identified and reported lesion at baseline and during follow-up. Imaging-based evaluation is preferred to evaluation by clinical examination unless the lesion(s) being followed cannot be imaged but are assessable by clinical exam.

Clinical lesions: Clinical lesions will only be considered measurable when they are superficial (e.g., skin nodules and palpable lymph nodes) and ≥ 10 mm diameter as assessed using calipers (e.g., skin nodules). In the case of skin lesions, documentation by color photography, including a ruler to estimate the size of the lesion, is recommended.

- **Time frame for obtaining measurements**

Patients will undergo imaging every two cycles of therapy ± 10 days until progression. In the event that patient discontinues treatment for reasons other than progression, imaging shall continue until progression on the same schedule employed while the patient was receiving treatment

- **Use of imaging techniques (e.g., x-ray, CT, MRI, PET) for measuring disease**

Chest x-ray: Lesions on chest x-ray are acceptable as measurable lesions when they are clearly defined and surrounded by aerated lung. However, CT is preferable.

Conventional CT and MRI: This guideline has defined measurability of lesions on CT scan based on the assumption that CT slice thickness is 5 mm or less. If CT scans have slice

thickness greater than 5 mm, the minimum size for a measurable lesion should be twice the slice thickness. MRI is also acceptable in certain situations (e.g. for body scans).

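### The primary ratio counts time on any therapy started after the study drug is stopped without progression, which objective 2.1.1 does not describe; the plan should state this rule and report the alternative beside it

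*Combined protocol and SAP*

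**What the plan says.** The objective and the operative definition differ.

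- **Objective 2.1.1** describes the ratio "as defined by the progression-free survival time on study treatment" over the corresponding time on the last treatment.
- **Sections 5.1.1, 8.1.4 and 14.2** take "the duration of time from start of treatment to the time of progression divided by the duration of time" measured from "the last treatment received pre-trial to the time of progression on that treatment". The denominator is tied to a named treatment; the numerator is not.
- **Evaluability (5.1.1):** "Those that die before progression or are lost to follow-up will be non-evaluable for the primary objective". Starting another therapy is not on that list.
- **Follow-up after stopping drug (8.1.2):** "imaging shall continue until progression on the same schedule employed while the patient was receiving treatment". Footnote f of the study activities table says the same. Section 6.3 lists reasons to stop other than progression, including unacceptable adverse events.
- **Later therapy:** footnote g says "Survival and information related to cancer treatment received after the study and disease status is monitored bimonthly", but no endpoint rule uses this information.
- **Re-registration (3.1.4):** "If a patient discontinues treatment on this protocol they can be considered for further participation in this trial", provided that the patient meets all eligibility criteria again and re-consents.
- **Best overall response (8.1.3)** is the best response from the start of treatment until progression or recurrence, again with no reference to a new therapy. Objective 2.2.1 asks for response on the off-label treatments.

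**The concern.** The ratio is meant to show how long the NGS-selected drug holds the disease compared with the previous treatment. For a patient who stops that drug early for a reason other than progression and then takes something else, the numerator also contains the effect of the later therapy. These patients remain evaluable, so they enter the median and the Wilcoxon test in full. A response first seen on the later therapy can likewise be counted as a response to the study drug. If such switching is common and the later therapy works, the primary result moves upward for a reason unrelated to the assigned drug, and a reader of objective 2.1.1 would not know it.

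**Working it through.** **1. The plan's own figures.** Inputs from 14.4: null ratio 1.0, alternative 1.3, SD 1.71, two-sided alpha 0.05, power 80%.

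- One-sample normal formula: n = (1.96 + 0.842)² × 1.71² / 0.3² = 255.0, rounded up to 256. The t-test version gives 257.
- Wilcoxon with normal data: 257 × π/3 = 269.1, against the stated 269.
- Total: 269 / 0.80 = 336.25, rounded up to 337, as stated.

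The sample size arithmetic is sound. The issue is the endpoint rule.

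**2. How the rule acts on one patient (invented figures).** Prior progression-free time 12 weeks; study drug stopped at week 4; another therapy started; progression at week 24. The ratio as written is 24/12 = 2.0, and 24 − 4 = 20 of the 24 weeks fall after the study drug was stopped.

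**3. Size of the bias in the median (assumed model).** Prior and study-drug times are independent Weibull (shape 1.3, median 12 weeks each), so there is no true effect and the true median ratio is 1.0. A fraction of those still progression-free at week 4 switch then, to a therapy with median 12–20 weeks. The share progression-free at week 4 is exp(−0.693 × (4/12)^1.3) = 0.85. Selecting 10%, 20% or 30% of those patients gives about 8.5%, 17% and 25% switching overall.

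| Switching | Median ratio, as written | Median ratio, ended at switch |
|---|---|---|
| about 8.5% | 1.01–1.05 | 0.89 |
| about 17% | 1.02–1.10 | 0.79 |
| about 25% | 1.04–1.15 | 0.69 |

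With a signed-rank test on log ratios at n = 269, false rejection under the rule as written runs from about the nominal 5% to about a third in the most extreme cell. Ended at the switch, it is roughly 30%, 75–80% and 97–98%, in the direction of harm.

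**4. Switchers alone, same model.** Their median ratio as written is about 1.4–2.1. Had they stayed on the study drug it would have been about 1.23, because they are selected for being progression-free at week 4. The excess in the median is therefore about 0.2 to 0.9 ratio units (1.4 − 1.23 to 2.1 − 1.23).

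**5. The same question under the plan's normal model.** Let a fraction f of the 269 gain g ratio units with no true effect, so that the mean shift is f × g.

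- f = 5%, g = 0.5: shift 0.025; rejection 5.6%.
- f = 10%, g = 1.0: shift 0.10, a third of the 0.3 target; rejection about 15%.
- f = 20%, g = 1.0: shift 0.20; rejection about 44%.

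Both f and g are assumptions. The documents fix neither.

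**6. Dropping switchers instead.** If 10% of the 337 became non-evaluable on top of the planned 20%, 337 × 0.70 leaves 235 patients, and power falls from 80% to 74.4%.

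**The case against.** Following patients to progression whatever they receive is a recognised strategy, and the continued imaging in 8.1.2 and footnote f shows that it is deliberate. Section 14.1 says that the trial evaluates an approach to assigning treatment, not a particular drug, so time on a second NGS-selected drug can be said to belong to the approach. The affected group may also be small: most patients will have been through two lines, or cannot or will not take standard therapy. Most of this stands, and it is why the rule should be kept as primary. It does not cover non-study therapy, and the plan nowhere states the choice, while 2.1.1 says something different.

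Three stronger readings are tempting, and the documents do not support them.

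- *The numerator should end at the switch.* This treats a switch as a progression, shortens one side of the ratio only, and enters what is really a censored time into the Wilcoxon test as complete. In the model above it lies further from 1.0 in every row.
- *The rule turns a failure into a benefit above 1.3, for example 2.0 in place of 4/12 = 0.33.* The 1.3 in 14.4 is the alternative used for power, not a per-patient threshold, and one patient hardly moves a median. Nor is 0.33 the right comparator: in the model, switchers would have had about 1.23 on the drug.
- *A patient can re-register without progression, and one progression then supplies two ratios.* Re-registration requires full eligibility again, and footnote a asks for imaging of progression within 60 days of registration, although an early stopper's original scan might still fall in that window. No section says that one patient gives two ratios; none rules it out either.

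**Conclusion.** The point holds as a mismatch between the objective and the operative endpoint, with an unstated rule for therapy started before progression. It affects only patients who stop the assigned drug without progressing and start something else before they progress; for them, later-therapy time and later-therapy responses are credited to the NGS-selected drug. Under the assumed no-effect model the median is overstated by 1% to 15%, so the bias is negligible to moderate. Its actual size depends on a switching rate and a next-line effect that the documents do not give. The primary rule can stay, provided that it is stated openly and its sensitivity to switching is shown.

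**What to change.** 1. Reword 2.1.1, and add a sentence to 5.1.1, 8.1.4 and 14.2, so that all four state that the primary numerator runs from start of treatment to progression regardless of later anticancer therapy.
2. Record the start date of any subsequent anticancer therapy, including a drug from a second registration. Pre-specify in 14.2 a sensitivity analysis with the numerator ended at that date, labelled a lower bound, and report how many patients it affects.
3. In 8.1.3, count toward best overall response only assessments made before another anticancer therapy starts.
4. State in 14.2 that each patient contributes one ratio, from the first registration.

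The cost is wording, one date field (the follow-up under footnote g already gathers later treatment), one extra analysis, and a response rate that may be slightly lower. Switchers stay evaluable, so 269 and 337 do not change.
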